5.2.6 Unscheduled Visits

Unscheduled visits may occur at any time at the investigator's discretion, and appropriate clinical and laboratory measurements performed based on AEs or other findings.

5.2.7 End of Treatment Visit (±14 days)

At the time of last study monitoring, loss of MMR, failure to achieve <MMR after 4 months or < MR^{4,5} after 6 months of combination treatment of PIO and TKI, the End of Treatment Visit should be completed for all subjects as soon as possible, and every effort should be made to perform the procedures required. Subjects will also return to the clinic or will be contacted for a safety follow-up assessment 30 days ± 3 days after the last dose of study drug was taken. Only information about AEs and SAEs will be collected at this visit.

The following procedures will be performed at End of Treatment Visit:

- Measure and record height in cm and weight in kg. Record vital signs. Measure body temperature, systolic / diastolic BP and pulse rate. Perform and record physical examination which is part of standard of care
- Record medications including start/stop dates, indication, dose and frequency for any changes since previous visit.
- Collect blood samples for CBC with differential count, blood chemistries, and qRT-PCR of *BCR/ABL1* as part of standard of care
- Collect blood samples for ABL1 domain mutation analysis as part of standard of care in case of loss of MMR
- Obtain all unused study drug if subjects drop out before discontinuation of PIO and TKI.
- Assess study drug compliance by pill count and review of the diary card
- Assess and record AEs and SAEs

5.3 *Subject Registration and Identification*

Demographic information on all subjects who sign the Informed Consent Form will be recorded on the master subject log. Those subjects who complete screening procedures and meet all eligibility criteria may be enrolled. At the time of registration, the subject will be assigned a unique identification code (number), consisting of a study site number and a unique consecutive number.

5.3.1 *Screen Failure*

Subjects who have signed informed consent and subsequently fail to meet the inclusion and/or exclusion criteria are defined as screen failures. For all screen failures, the Investigator is to maintain a screening log that documents the subject initials and reason(s) for screen failure. A copy of the log will be retained in the Investigator's study files. Any subject who is rescreened after screen failure must, in addition to the failed procedure, repeat only those screening procedures outlined in the Schedule of Events that have fallen outside the specified screening period.

5.3.2 *Early Discontinuation*

In the event that a subject is withdrawn from the study, every effort will be made by the Investigator to document and report the reasons for withdrawal as thoroughly as possible. The reason(s) for termination must be clearly reported in the subject's CRF. An End-of-Treatment reason for discontinuation must be recorded for any subject who is registered. If a subject is discontinued from the trial for any reason, every effort must be made to perform all clinical and laboratory procedures as scheduled for the End-of-Treatment Visit. In the event that the subject fails to return for the necessary visit(s), an effort must be made to contact the subject to determine the reason, and this information should be recorded in the appropriate source record and the end-of-treatment CRF.

5.4 *Study Duration*

The total estimated duration of the study is 5 years, including 2 years to accrue subjects, and 3 years of follow up for the last subject enrolled. Subjects will be supplied the study drug PIO until they discontinue treatment.

5.5 *Withdrawal Criteria*

Subjects will be discontinued from further study drug administration if any of the following occur:

- Loss of MMR at any time
- Subjects entering the study in > MMR but still in CCyR and CHR who do not achieve MMR within 4 months of the combination of PIO and TKI
- Subjects who fail to achieve < MR^{4,5} after 6 months of the combination of PIO and TKI
- Intolerable toxicity as determined by the Investigator or the subject
- Any grade 3 or higher cardiac toxicity
- Any grade 4 toxicity possibly associated with PIO
- A treatment interruption for study-drug related non-hematologic toxicities lasting > 28 days
- Intolerance to PIO
- Significant deviation from the protocol or eligibility criteria
- Noncompliance with study or follow-up procedures
- Pregnancy
- Subject withdrawal of consent and decision to discontinue participation
- Termination of the trial
- Any other reason that, in the opinion of the Investigator, would justify removal of the subject from the study

5.6 *Study Termination*

If the sponsor-investigator, Data Monitoring Committee, or regulatory agencies discover conditions during the study that indicate that the study should be terminated, this action may be taken after appropriate consultation between the sponsor-investigator, and Data Monitoring Committee. Conditions that may warrant termination of the study include, but are not limited to:

- The discovery of a serious, unexpected, or unacceptable risk to subjects enrolled in the study
- Submission of knowingly false information from the research facility to the regulatory authorities
- Insufficient adherence to protocol requirements

Study termination and follow-up will be performed in compliance with the conditions set forth in the guidelines for Good Clinical Practice (**GCP**), International Conference on Harmonization (**ICH**) of Technical Requirements for Registration of Pharmaceuticals for Human Use.

6. Safety Assessments

Safety Assessments: Safety will be assessed by routine physical and laboratory evaluations according to the schedule (**Table 3**) and as medically indicated. AEs will be recorded and the severity will be graded according to the CTCAE v.4.03.

Adverse Events: Type, incidence, severity (graded in accordance with the CTCAE v.4.03), timing, seriousness and relatedness, outcome, action taken with study drug, and treatment will be assessed and documented by the investigator continuously throughout the study. Baseline malignancy-related signs and

symptoms will be recorded as AEs during the study if they worsen in severity or increase in frequency. Procedures for following AEs at the end of treatment and beyond are outlined in Section 5.1.

7. Study Treatment

Subjects will be provided with the study drug PIO to take in addition to TKI. The TKI that was previously discontinued will be restarted at doses administered prior to the first discontinuation. PIO will be self-administered on a once daily schedule.

7.1 Dose Selection, Treatment Administration, Compliance, and Dose Modifications

The starting dose of PIO will be 30 mg and will be taken orally once daily. After 56 days of PIO 30 mg/d, the dose will be increased to 45 mg/d in the absence of grade >1 related AE. The dose of PIO was selected based on previously published pilot report [47].

Subjects will take the prescribed tablets at approximately the same time each day, regardless of meals. Subjects will be provided a diary card where the date and time of administration will be recorded (**Appendix 1**). Subjects who forget to take their dose can make up the missed dose as long as this is done within the 12 hours of the due time. Any missing dose should be recorded. Drug compliance will be measured using the Morisky Medication Adherence Scales-8 (MMAS8) at every visit while on PIO and TKI (**Appendix 2**). Dose modification will be done as follows:

Table 4. Dose Modification

Toxicity		Immediate action	Later action
Hematologic toxicity	≥ Grade 3 Neutropenia or Thrombocytopenia	1. Hold PIO and TKI until ≤ Grade 1	1. First episode: resume TKI and PIO without dose modifications 2. Second episode: resume at 1 lower dose level (previous dose -15 mg) 3. Third episode: permanent discontinuation of PIO, resume TKI alone
	≤ Grade 3 anemia	1. Continue PIO 2. RBC transfusion if indicated	1. First episode: resume TKI and PIO without dose modifications 2. Second episode: resume PIO at 1 lower dose level (previous dose -15 mg) 3. Third episode: permanent discontinuation of PIO, resume TKI alone
	Grade 4 anemia	1. Hold PIO and TKI 2. RBC transfusion if indicated	1. First episode: resume PIO at 1 lower dose level (previous dose -15 mg) 2. Second episode: permanent discontinuation of PIO, resume TKI alone
Non-hematologic toxicity	Grade 2	1. Hold PIO until ≤ Grade 1	1. First episode: resume TKI and PIO without dose modifications 2. Second episode: resume at 1 lower dose level (previous dose -15 mg)
	≥ Grade 3*	1. Hold PIO and TKI until ≤ Grade 1	1. First episode: resume PIO at 1 lower dose level (previous dose -15 mg) 2. Second episode: permanent discontinuation of PIO, resume TKI alone

*In case of cardiac toxicity, subject will be taken off the study

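### Table 4 restarts pioglitazone after a first grade 4 event, while section 5.5 stops it for good if the event is possibly associated with the drug; section 3.1 adds a second, different dose rule

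*Combined protocol and SAP*

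**What the plan says.** Table 4 (section 7.1) has five rows. Three include grade 4 events, and each restarts PIO after a first episode:

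- The row headed "≥ Grade 3 Neutropenia or Thrombocytopenia" holds both drugs ("1. Hold PIO and TKI until ≤ Grade 1") and then directs "First episode: resume TKI and PIO without dose modifications". PIO is lowered at the second episode and ends only at the third ("Third episode: permanent discontinuation of PIO, resume TKI alone").
- The grade 4 anemia row holds both drugs ("1. Hold PIO and TKI 2. RBC transfusion if indicated") and then directs "First episode: resume PIO at 1 lower dose level (previous dose -15 mg").
- The non-hematologic grade 3 or higher row also holds both drugs, to grade 1 or lower, and gives the same first-episode action. In this row and the grade 4 anemia row the next step is "Second episode: permanent discontinuation of PIO, resume TKI alone".

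The table's single footnote takes subjects with cardiac toxicity off study. No row mentions attribution to PIO or refers to 5.5.

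Section 5.5 opens with "Subjects will be discontinued from further study drug administration if any of the following occur" and lists any grade 4 toxicity possibly associated with PIO.

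Section 3.1 says that after a grade 2 or higher toxicity on 45 mg/d, PIO is held until grade 1 or lower and then reduced to 30 mg/d. The same sentence points to 7.1 for dose modification.

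**The concern.** Table 4 is what a treating physician will consult when a toxicity occurs. For a grade 4 event possibly associated with PIO, the table leads to re-exposure and 5.5 leads to a permanent stop. Section 12.4 ends the trial once more than two subjects have such an event, so the protocol clearly regards these events as grave.

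The 3.1 difference concerns the dose given after more common, lower-grade events. It also has a small analytic side. Section 9.2 lists giving an incorrect study drug dose as a major violation that removes a subject from the per-protocol population. Where two sections prescribe different doses, a subject dosed correctly under one can be called a violator under the other.

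**Working it through.** No statistical figure is involved. The check sets the three rules side by side for a first episode in a subject on 45 mg/d. Inputs are Table 4 (7.1), the hold-and-reduce sentence in 3.1, and the grade 4 criterion in 5.5.

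| Table 4 row | Table 4: PIO at first episode | 3.1: PIO | 5.5, if grade 4 and possibly associated with PIO |
|---|---|---|---|
| Neutropenia/thrombocytopenia, grade 3 or higher | hold, then 45 | hold, then 30 | stop |
| Anemia, grade 3 or lower | continue at 45 | hold, then 30 (if grade 2 or 3) | not applicable |
| Anemia, grade 4 | hold, then 45 − 15 = 30 | hold, then 30 | stop |
| Non-hematologic, grade 2 | hold, then 45 | hold, then 30 | not applicable |
| Non-hematologic, grade 3 or higher (non-cardiac) | hold, then 45 − 15 = 30 | hold, then 30 | stop |

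**Against 5.5.** Rows that include grade 4: 3 of 5. Of these, rows that restart PIO after the first episode: 3 of 3 (at 45, 30 and 30 mg/d). In the neutropenia/thrombocytopenia row Table 4 permits two restarts, the second at 45 − 15 = 30 mg/d, where 5.5 permits none.

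**Against 3.1.** Rows that differ at the first episode: 3 of 5 (neutropenia/thrombocytopenia, lower-grade anemia, grade 2 non-hematologic). The size is 45 − 30 = 15 mg/d, and 15/45 = 33%. In the other two rows the PIO dose agrees. At a second episode from 45 mg/d the resumed dose also agrees in the three differing rows (45 − 15 = 30), although for anemia of grade 3 or lower Table 4 still does not hold PIO.

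**Recovery grade.** Rows with a hold: four (the three that include grade 4, plus grade 2 non-hematologic). All but grade 4 anemia state grade 1 or lower, so 1 of 4 lacks it. Section 3.1 would supply that threshold, but only for PIO and only on 45 mg/d. If the 3.1 rule is deleted, nothing supplies it.

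**TKI restart.** Rows that hold both drugs: three. The first-episode cell names the TKI in one (neutropenia/thrombocytopenia) and omits it in two (grade 4 anemia, non-hematologic grade 3 or higher).

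**The case against.** The best reply is that 5.5 and Table 4 can be read together. Section 5.5 is mandatory and sits above the table; on that view it governs grade 4 events possibly associated with PIO, and Table 4 governs the rest. Other text leans that way. Section 12.4 counts these events toward termination, and the severity definitions in 8.1.5, for events not defined in CTCAE, treat grade 4 as requiring discontinuation. Table 4 also omits 5.5's 28-day limit on interruptions, and nobody would take that as leave to exceed it. Section 9.6 further limits the consequence by putting the trial on hold when grade 3-4 toxicity is seen in two subjects. This is a sensible reading and probably the intended one, but the table does not state it, and a trial-level hold does not decide what one subject takes next. Table 4 writes out a cardiac exception, so its silence on PIO-associated grade 4 events invites the opposite reading.

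On 3.1, the cross-reference to 7.1 suggests that Table 4 was meant to supply the detail. That stands, and it is why letting the table govern is the natural repair. It does not remove the conflict, because 3.1 states its own rule and no precedence is given.

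A reader might infer from the two cells that omit the TKI that PIO is to be restarted alone in subjects who have already lost major molecular response off TKI. The documents do not support this. Section 7 gives PIO on top of the TKI, and where Table 4 means one drug it says so. Its wording on resumption is also loose elsewhere: the grade 2 row holds only PIO yet speaks of resuming both. The TKI dose is set at study entry in 3.3 and 7, so the same dose is the obvious default.

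**Conclusion.** The conflict with 5.5 is real as written and is the main point: three of five rows, opposite instructions, one of them a restart at the unchanged dose. The 3.1 conflict is also real and reaches three rows, by 15 mg/d at a first episode on 45 mg/d. The missing recovery grade for grade 4 anemia and the omitted TKI restart are minor.

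Two assumptions matter. First, how widely 5.5 reaches depends on how its attribution phrase is read. If it follows the possibly-related category in 8.1.6, it takes in events with another equally likely cause, such as a cytopenia equally likely due to the TKI; the protocol does not make that link explicit. Second, the documents give no rates of these events on the combination, so the number of affected subjects cannot be estimated; counts of rows describe the text, not the frequency.

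A reader might also infer that the plan intends rechallenge after PIO-associated grade 4 toxicity, or that the sample size or stopping boundaries are affected. Neither follows. The first is contradicted by 5.5 itself, and the second does not depend on these dosing rules.

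**What to change.** 1. Add a footnote to the three rows that include grade 4: grade 4 events possibly associated with PIO are handled under 5.5, and PIO is not restarted.
2. Delete the hold-and-reduce rule from 3.1, keep the reference to 7.1, and let Table 4 govern. If the clinical team prefers the 3.1 rule, change all three affected rows; aligning only the grade 2 non-hematologic row would leave the neutropenia/thrombocytopenia and lower-grade anemia conflicts in place.
3. Give the grade 4 anemia hold a recovery grade, for example grade 1 or lower as in the other hold rows, to be confirmed by the clinical team. This becomes necessary if the 3.1 rule is removed.
4. In the grade 4 anemia and non-hematologic grade 3 or higher rows, state at the first episode that the TKI resumes at its pre-hold dose and PIO one dose level lower.

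The cost is revised wording in one table, one footnote and one sentence in 3.1 (or three rows, if the alternative in item 2 is chosen). No visits, tests or subjects are added.

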7.2 Allocation of Treatment

The results of screening assessments for each subject will be reviewed by the study principal investigator (PI), who will approve each subject. Upon this approval, subjects will receive a 28 days (1 cycle) + 2 days supply of 30 tablets of PIO.

7.3 Concomitant Medications

All concomitant medications administered from the time of informed consent signature through 30 days after the end of treatment (last dose or investigator/subject decision to discontinue, whichever is later) are to be reported on the CRF for each subject. No medications will be prohibited, but caution will be used for medications that interact with PIO according to the package insert.

7.4 Treatment Supply:

7.4.1 Formulation, Packaging and Labeling:

PIO will be purchased by the Investigational Pharmacy at Emory for use in this trial. PIO is available as a tablets for oral administration containing 15, 30, and 45 mg of PIO (as the base) formulated with the following excipients: lactose monohydrate NF, hydroxypropylcellulose. Tablet will be supplied as follows: 30 counts in Rexam's 1-ClicR vials (Rexam PLC, London, UK) that comes with induction-sealed child resistant caps. Bottle labels will bear the appropriate label text as required by governing regulatory agencies, to include product name, product strength, number of capsules, and lot number.

7.4.2 Treatment Storage, Dispensing, and Accountability

The recommended storage condition for PIO is room temperature (15-30°C), and should be kept in the original container to protect from light and from humidity. The study pharmacist or designee at the site will be responsible for handling, dispensing study drug, completing associated documentary paperwork, handling dispensing log/accountability form. Each time study medication is dispensed for a subject, the following information will be recorded: the subject's initials, the subject's study number, tablet strength, the number of tablets dispensed with the corresponding lot number, and the initials of the person dispensing the drug. These logs are to be maintained by the study pharmacist in the pharmacy throughout the duration of the study. The Investigator is responsible for ensuring that the subject diary card(s) and study drug provided to the subject and returned from the subject are accounted for and noted in source documentation.

7.4.3 Disposition of used and unused supplies

All used bottles or packs of study drug must be destroyed according to the standard practice. Destruction of such supplies will be documented. During the trial and at termination, subjects must return all unused study drug supplies and the return of these unused study drug supplies must be recorded. Returned supplies must not be re-dispensed. No other utilization of PIO intended for use in this study will be authorized. The investigator or his/her designee will be responsible for the appropriate handling and disposition of residual study drug.

8. Adverse Event Reporting

8.1 Adverse Events

8.1.1 Adverse Event Definition

An AE is any untoward medical occurrence in a subject or clinical investigation subject administered a pharmaceutical product which does not necessarily have to have a causal relationship with this treatment. An AE can be any unfavorable and unintended sign (including an abnormal laboratory finding), symptom, or disease temporally associated with the use of a medicinal product whether or not considered related to the medicinal product. Any worsening of a preexisting condition, which is temporally associated with the use of the study drug (i.e., occurs after the first dose of study drug), is also an AE. AEs include:

- Abnormal test findings
- Changes in physical exam findings
- Other untoward medical events, regardless of their relationship to the study drug, such as injury, events that require surgery, accidents, or apparently unrelated illnesses, and hypersensitivity
- AEs may include signs or symptoms resulting from: drug overdose, drug withdrawal, drug abuse, drug misuse, drug interactions, drug dependency, and, in utero drug exposure

8.1.2 Abnormal Laboratory Tests

The criteria for determining whether an abnormal objective test finding should be reported as an AE are as follows:

- Test result is associated with accompanying symptoms that are considered clinically significant in the opinion of the investigator
- Test result requires additional diagnostic testing (other than merely repeating an abnormal test) or medical/surgical intervention
- Test result leads to a change in study drug dosing or discontinuation from the study, significant additional concomitant drug treatment, or other therapy
- Test result is considered to be an AE by the investigator

8.1.3 Performing Adverse Event Assessment

All observed or volunteered AEs, regardless of suspected causal relationship to the investigational product, will be reported as described in the following sections. For all AEs, the investigator must pursue and obtain information adequate to determine the outcome of the AE and to assess whether it meets the criteria for classification as a serious AE requiring immediate notification to the appropriate regulatory agencies.

8.1.4 Reporting Period

Serious AEs require notification of the appropriate regulatory agencies beginning from the time the subject starts receiving the investigational product, through and including 30 days after the last

administration of the assigned study treatment or the investigator/subject decision to discontinue treatment, whichever occurs later. Any SAE occurring any time after the reporting period must be promptly reported if a causal relationship to the investigational product is suspected. Any SAE ongoing at the end of the reporting period should be followed as described below. For all enrolled subjects, AEs (serious and non-serious) should be recorded on the CRF beginning with the signing of the informed consent form and concluding 30 days following the last dose of the assigned study treatment or the investigator/subject decision to discontinue treatment, whichever occurs later. AEs ongoing after the reporting period: Any ongoing AEs thought to be at least possibly study-drug related and all ongoing SAEs after this time should be followed at least every 4 weeks until they resolve to baseline (or CTCAE grade ≤ 1), stabilize, or are considered to be chronic/irreversible.

8.1.5 Adverse Event Severity

The severity of AEs will be assessed according to the CTCAE, v.4.03 If the AE is not defined in the CTCAE, the investigator will determine the severity of the AE based on the following definitions:

- Mild (grade 1): The AE is noticeable to the subject but does not interfere with routine activity. The AE does not require discontinuing administration or reducing the dose of the study drug
- Moderate (grade 2): The AE interferes with routine activity but responds to symptomatic therapy or rest. The AE may require reducing the dose, but not discontinuing administration of the study drug
- Severe (grade 3): The AE significantly limits the subject's ability to perform routine activities despite symptomatic therapy. In addition, the AE leads to discontinuing administration or reducing the dose of the study drug
- Life-Threatening (grade 4): The AE requires discontinuing administration of the study drug. The subject is at immediate risk of death
- Death (grade 5): The subject dies as a direct result of the complication or condition induced by administration of the study drug

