- Review and document all inclusion and exclusion criteria to ensure that subjects meet all inclusion criteria and none of the exclusion criteria.
- Record AEs as part of standard of care.
- Dispense PIO at 30 mg/d and instruct subjects how to take study drug, daily every 24 hours and how to fill the diary card.

5.2.3 **Visits 3 (Days 14 \pm 2): Early Follow-up**

- Measure and record height in cm and weight in kg. Record vital signs. Measure body temperature, systolic/diastolic BP and pulse rate. Perform and record physical examination.

- Record medications including start/stop dates, indication, dose and frequency for any changes since previous visit.
- Collect blood samples for CBC with differential count and serum chemistries.
- Assess study drug compliance by pill count, review of the diary card and MMAS-8.
- Assess and record AEs and SAEs

5.2.4 Visits 4+ (Day 28 ±2, then q28+/-2 days during combination of PIO and TKI)

- On day 28, measure and record height in cm and weight in kg. Record vital signs. Measure body temperature, systolic / diastolic BP and pulse rate. Perform and record physical examination. Unless new symptoms occur, these will be performed every other month as part of standard of care.
- On day 28, record medications including start/stop dates, indication, dose and frequency for any changes since previous visit. Unless new symptoms occur, these will be performed every other month as part of standard of care.
- On day 28, collect blood samples for CBC with differential count and serum chemistries. Unless new symptoms occur, these will be performed every other month as part of standard of care.
- On day 56, in the absence of grade 2 or higher toxicities, PIO doses will be increased to 45 mg/d
- Dispense drug supply for self-dosing, remind subjects of dosing instructions, and obtain all unused study drug
- Assess study drug compliance by pill count, review of the diary card and MMAS-8.
- Collect blood samples for qRT-PCR of *BCR/ABL1* every month.
- Assess and record AEs and SAEs continuously

5.2.5 Post-discontinuation of PIO and TKI Visits (Monthly for 3 months ± 2 days and quarterly ±7 days for 1 year and biannually thereafter)

- Collect blood samples for qRT-PCR of *BCR/ABL1* as part of standard of care
- Assess and record AEs and SAEs continuously

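### For adverse events outside CTCAE, the fallback severity scale makes a pioglitazone dose change a condition of grade 3 and drug causality a condition of grade 5, so some events have no valid grade

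*Combined protocol and SAP*

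**What the plan says.** CTCAE v4.03 is the governing scale throughout. Section 8.1.5 adds a fallback for the remainder: "If the AE is not defined in the CTCAE, the investigator will determine the severity of the AE based on the following definitions". The fallback grades that matter here are:

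- Grade 2: "The AE interferes with routine activity but responds to symptomatic therapy or rest. The AE may require reducing the dose, but not discontinuing" the drug.
- Grade 3: "The AE significantly limits the subject's ability to perform routine activities despite symptomatic therapy", followed by "In addition, the AE leads to discontinuing administration or reducing the dose of the study drug".
- Grade 4: "The AE requires discontinuing administration of the study drug. The subject is at immediate risk of death".
- Grade 5: "The subject dies as a direct result of the complication or condition induced by administration of the study drug".

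Table 4 in section 7.1 runs from grade to action. For non-hematologic toxicity of grade 3 or higher, the immediate step is "Hold PIO and TKI until ≤ Grade 1". The later step is a lower PIO dose after a first episode and permanent discontinuation after a second.

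AEs are also collected when no PIO is being taken. Section 8.1.4 records them from signature of consent until 30 days after the last dose or the decision to stop, whichever is later. Section 5.2.5, on visits after PIO and TKI have been stopped, says "Assess and record AEs and SAEs continuously".

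Section 6 lists severity, relatedness and action taken with study drug as separate items to be documented for each AE.

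**The concern.** A severity grade should describe what happened to the subject. Here two other things enter it: what was done with the drug (grade 3, and in part grades 1, 2 and 4) and whether the drug was the cause (grade 5).

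Two problems follow. First, the grade is meant to determine the dose action, yet on this scale the action helps to determine the grade. Two subjects with the same limitation could be graded differently because one of them stopped PIO. Second, an event that arises with no PIO dose left to reduce or stop cannot satisfy the dose element, however disabling it is.

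Safety is part of the primary endpoint (9.3), and AE incidence is to be described by grade (9.5). Section 9.6 puts the trial on hold once grade 3-4 toxicity has been seen in 2 subjects, so a missing grade could matter to that rule.

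**Working it through.** The plan states no figure on this point, so the check is mainly a comparison of text. A short illustration of size follows.

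**1. Is the dose action a criterion or a remark?** The grade 3 text gives the functional limitation first and joins the dose action to it with words of addition. On its wording both are required. Grades 1, 2 and 4 also mention dose action, but without that explicit joining phrase.

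**2. Direction of dependence.** In 8.1.5, grade 3 needs a PIO reduction or stop. In Table 4, a PIO reduction or stop follows from the grade. The link is not exclusive. Section 5.5 lets PIO be stopped for toxicity that the investigator or the subject finds intolerable, with no grade required. Table 4 also holds PIO at non-hematologic grade 2 and lowers it at a second such episode. A dose action can therefore come before a grade 3 assignment. The dependence is partial.

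**3. Does dose action separate the grades?** It does so poorly. Grade 2 in 8.1.5 also permits a reduction. In the other direction, Table 4 resumes PIO unchanged after a first episode of grade 3 or higher neutropenia or thrombocytopenia.

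**4. A functionally severe event with no PIO being taken.** Take an event that CTCAE does not define, that markedly limits routine activity despite symptomatic therapy, that is not immediately life-threatening, and that arises before Day 1 or after the last dose.

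| Fallback grade | Met? | Reason |
|---|---|---|
| 1 | No | Requires no interference with routine activity |
| 2 | No | Requires response to symptomatic therapy or rest |
| 3 | No | Functional element met; no PIO dose to reduce or stop |
| 4 | No | No immediate risk of death |
| 5 | No | Not fatal |

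The event has no valid grade.

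**5. A death from another cause.** Grade 5 requires a complication or condition induced by the study drug. A death from an event on this scale that the investigator judges unrelated does not qualify, although 8.1.6 assesses causality separately for every AE.

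**6. Size of the effect on the 9.6 hold.** Let X be the number of subjects with recognised grade 3-4 toxicity. Assume independent subjects with a common true rate p, and let a share s of the affected subjects lose their qualifying grade. Then X ~ Binomial(26, p(1 − s)), and

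P(hold) = 1 − (1 − q)^26 − 26q(1 − q)^25, with q = p(1 − s).

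Example: for p = 0.10 and s = 0.05, q = 0.095 and P(hold) = 0.722. The documents give neither p nor s, so a range is shown.

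| p | s = 0 | s = 5% | s = 10% | s = 25% |
|---|---|---|---|---|
| 5% | 0.376 | 0.352 | 0.328 | 0.255 |
| 10% | 0.749 | 0.722 | 0.692 | 0.591 |
| 20% | 0.977 | 0.970 | 0.961 | 0.918 |

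At s = 5% the fall is 0.024, 0.027 and 0.007 respectively. It becomes sizeable only if a large share of severe events lies outside CTCAE and in the gap.

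**The case against.** The strongest reply is that this is a loosely worded backstop that will seldom be used. Several parts of it stand:

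- CTCAE governs, and the documents identify no particular AE that would fall outside it.
- The loop between grade and action is open, as steps 2 and 3 of the working show. A reader might infer that grade and action each wait for the other and neither can ever be set. Sections 5.5 and 7.1 do not support that.
- Seriousness under 8.2.1 does not depend on grade. Life-threatening events, hospitalizations, incapacity and important medical events are captured as SAEs, as is any death within 30 days of the last dose regardless of cause.
- The grade 5 wording does not reach the 9.6 hold, which names grades 3-4 only.
- An event before Day 1 could hardly count as toxicity under 9.6. For the hold, only the period after the last dose is relevant.

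One could also read the grade 3 dose sentence as describing the usual consequence of a severe event. That is a sensible reading of intent, but the sentence is written as an added condition, and a grader following it literally reaches the gap in step 4. SAE capture does not fill that gap either, because the tables in 9.5 and the hold in 9.6 run on grade.

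**Conclusion.** The point holds as a drafting defect of small likely impact. For AEs that CTCAE v4.03 does not define, and only for those, 8.1.5 adds a PIO dose action to grade 3 and drug causality to grade 5. Read literally, this leaves functionally severe events off PIO, and unrelated deaths, without a grade. The affected outputs are the graded AE tables in 9.5 and, for grades 3-4, the hold in 9.6. The conclusion rests on reading the added grade 3 sentence as a requirement. The size rests on the assumed values of p and s.

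Four stronger readings are tempting, and the documents do not support them:

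- That grade 3 is defined by dose action alone. The functional element comes first and is also required.
- That no event after the last dose can be graded severe. Events that CTCAE defines can be graded at any time.
- That severe events are systematically under-graded. The text leaves them ungraded and does not send them to a lower grade.
- That the cardiac stopping rules in 9.4 and 12.4 are compromised. That would need a cardiac event outside CTCAE, and the documents point to none.

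**What to change.** In 8.1.5, define fallback grades 1 to 5 by clinical effect on the subject only. Remove dose action as a grading criterion, and remove from grade 5 the condition that the study drug caused the death. Record action taken with study drug and relatedness as separate items. Section 6 already lists both, so no new data are needed.

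Separately, the sponsor must reconcile what the protocol says on holding, reducing or stopping PIO. The grade 4 text in 8.1.5 calls for discontinuation. Section 5.5 withdraws subjects from study drug for grade 4 toxicity possibly associated with PIO. The Table 4 row for non-hematologic grade 3 or higher allows PIO to be resumed at a lower dose after a first episode. This review does not propose which of these should prevail.

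The grading change costs wording only and does not affect sample size or analysis method. A few events may receive a grade, or a higher grade, that they would not get on the present text. Any event already graded on the fallback scale should be reread against the new wording.
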